2. OBJECTIVES AND ENDPOINTS

2.1 Primary Objectives

Randomisation-1: bpMRI versus mpMRI

IP7-PACIFIC Protocol No: 22CX7488	Imperial College London	V3.0 18 th December 2023
-----------------------------------	-------------------------	-------------------------------------

In those patients suspected to have prostate cancer, to determine whether bi-parametric MRI (bpMRI), compared to multi-parametric MRI (mpMRI), is able to accurately rule-out and detect clinically significant prostate cancer (any Gleason score >/=7 [ISUP Grade Group >/=2]), without increasing the number of patients biopsied or diagnosed with clinically insignificant prostate cancer.

Randomisation-2: Visual-registration targeting versus image-fusion targeting

In those patients recommended to have a prostate biopsy due to a suspicious MRI (bpMRI or mpMRI), to determine if new technology using MRI to ultrasound image-fusion to carry out targeted prostate biopsies is better at detecting clinically significant prostate cancer (any Gleason score >/=7 (any Gleason score >/=7 [ISUP Grade Group >/=2]), compared to biopsies carried out using visual-registration targeting.

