Reporting scheme: NICE currently recommends the use of the Likert scoring system with data showing its equivalence to PIRADS scoring. Our systematic review showed that of 44 studies, 21 used Likert scoring and 14 used PIRADS scoring with the other studies not stating the scoring system they used. In the PIRADS and Likert scoring systems, contrastenhancement is used in interpreting equivocal lesions. Since neither PIRADS or Likert can be fully applied for bpMRI, and as there is current heterogeneity of MRI scoring practice and uncertainty around which scoring system to use, we propose that both PIRADS (as per latest version determined in the MRI SOP) and Likert should be used in bpMRI and mpMRI evaluations. Our UK clinician survey indicated that 40% use Likert scoring and 53% use PIRADS; all who agreed to take part in the study also agreed to report both scores in the study.

Decision for biopsy

Decision to recommend biopsy: The decision-making around which groups of patients to recommend a biopsy will be in concordance with NICE guidance 2019 and reflect the

IP7-PACIFIC Protocol No: 22CX7488	Imperial College London	V3.0 18 th December 2023
-----------------------------------	-------------------------	-------------------------------------

majority of our clinicians' view in our recent survey. We have wide clinical consensus that those patients with a suspicious MRI (score 4 and 5 on either Likert or PIRADS [latest version as defined in MRI Reporting SOP]) should be advised to undergo a biopsy. Patients with a non-suspicious (score 1, 2) or equivocal MRI (score 3) (on either Likert or PIRADS [latest version as defined in MRI Reporting SOP]) with one or more risk factors (PSA density >/=0.12ng/ml/ml or >/=0.15ng/ml/ml, family history or ethnic risk) may also be recommended to have a biopsy. Normal practice at each centre will be declared prior to study recruitment. We shall report the number of patients recommended for biopsy included in the analysis who had a non-suspicious bpMRI/mpMRI and of these, the numbers of clinically significant and clinically insignificant cancers subsequently detected. We shall also report the number of patients who were recommended to have a biopsy but chose not to have it.

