Follow-up of patients not undergoing a biopsy: Patients will be discharged back to the GP by their clinical team after their MRI with individual advice about the level of PSA that should lead to a referral back to hospital. Sometimes the clinical team reviews a patient 6-12 months later with another PSA level. The NICE guidance have set out key parameters for follow-up within primary or secondary care for patients who do not have a biopsy or end up with a negative biopsy and this will be the approach we advise centres to take (see sections 1.2.10-1.2.13, 9th May 2019, NICE Guidance NG131 [4]). Some patients with significant lower urinary tract symptoms will need ongoing follow-up and care as well as any relevant procedures for benign prostatic hyperplasia. The trial protocol will not stipulate the type of follow-up that occurs after biopsy as this is beyond the remit of the current proposal. We will collect information on whether additional tests or procedures were carried out within the 3 months of trial follow-up using our patient questionnaire. Future long-term outcomes through national database linkage will be collected, however, only if funding for such research activity is successful.

Randomisation-2: Visual-registration targeting versus image-fusion targeting

Targeted biopsy with either commercially available CE-marked image-fusion devices or visual-registration. The study will pragmatically permit any CE-marked image fusion device depending on local availability. For centres that do not have image-fusion devices, we have incorporated costs for hiring these for centres. All patients will undergo non-targeted systematic </=12 core biopsies or transperineal sectoral biopsies as well. The type of systematic biopsy approach will need to be declared by each centre at the beginning of the study and reasons for deviations from the standard systematic biopsy approach will be collected.

Biopsy

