For each randomisation, the number and proportion of clinically significant cancers detected in the randomised population will be reported by trial arm. Group differences will be quantified by the risk difference with two-sided confidence intervals at a level appropriate to the significance level pre-specified in the sample size. Detection rates will be compared by trial arm using mixed models with adjustment for trial arm allocation of co-enrolled trial and random effect by centre. The treatment effect coefficients will be presented with confidence intervals and associated p-value. The primary analysis will be conducted on an intention-totreat (ITT) basis, where patients with missing outcomes are assumed not to have clinically significant prostate cancer. A modified ITT analysis will be performed excluding patients who did not complete the diagnostic tests, and for the non-inferiority comparison a per protocol analysis including only those undergoing randomly assigned interventions. A pre-specified statistical analysis plan will be drafted detailing intended analyses for primary and secondary outcomes. It will be approved by the IDMC and agreed prior to analysis.

Cost-effectiveness analysis

A within trial cost-effectiveness analyses will estimate the incremental cost per true positive detected and incremental cost per correct diagnosis. Estimates of diagnostic performance will be based on the trial analysis and costs will be estimated from the NHS and PSS perspective using a micro-costing approach for tests. Deterministic (to explore plausible alternatives e.g., quantity of resources used or unit costs) will be combined with stochastic

IP7-PACIFIC Protocol No: 22CX7488	Imperial College London	V3.0 18 th December 2023
-----------------------------------	-------------------------	-------------------------------------

sensitivity analysis (used to explore statistical imprecision in estimates of costs, effects and cost-effectiveness).

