Our proposed study design is a non-inferiority study. However, it is only non-inferior with respect to the primary outcome and one form of imaging may be superior in other aspects (for example one form of imaging may be less costly). It is possible that even though the study is designed to be a non-inferiority study that clinically important differences may not be ruled out by the final analysis. To mitigate against this possibility and still provide information to guide NHS-decision making we propose to conduct (as described below) a cost-utility analysis.

The proposed economic evaluation work described below will also allow us to consider whether the resource implications of adopting a potentially less time-consuming imaging methods as well as any knock-on effects elsewhere in the system caused by changes in the imaging process.

Within trial analysis

A within trial cost-effectiveness analyses will estimate the incremental cost per true positive detected and incremental cost per correct diagnosis. Estimates of diagnostic performance will be based on the trial analysis and costs will be estimated from the NHS and PSS perspective. The costs of the tests will be based upon a micro -costing approach for tests. Costs components will include cost of staff time to deliver and interpret the tests. In sensitivity analysis we will also consider the additional costs of training additional health

personnel, and the time spent in familiarising with the technology. Data on the resources needed to deliver and interpret the tests will be collected via a case report form and from study centres. Other care provided up to the end of the trial follow-up will also be collected via a case report form.

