We anticipate a Discrete Event Simulation (DES) [Karnon et al, 2012] will be used as the model will explore the impact of allowing more patients to be imaged to determine the long-term impact on services later in the care pathway. However, the precise form of the model will be developed during the course of the study to best address the decision problem and we shall draw upon the advice of the clinical study teams and PPI Group. The model structure is likely to include a short-term decision tree element where that mirrors the within trial analysis and reports costs and outcomes up to the management decision following imaging e.g. biopsy or not. The model will then extrapolate the impact on patients' health (measured in QALYs) and NHS and PSS costs as a consequence of that decision. This will include the impact of 'incorrect or sub-optimal' decisions and the impact of correct decisions. The model will include subsequent treatment/management of prostate cancer, and the impact of recurrence or progression and subsequent management.

Stakeholders and literature reviews will inform the structure of the model. Data from the trial and secondary sources such as existing systematic reviews, primary evidence and other

IP7-PACIFIC Protocol No: 22CX7488	Imperial College London	V3.0 18 th December 2023
-----------------------------------	-------------------------	-------------------------------------

economic evaluations conducted in the area of prostate cancer research will be synthesised to build and parametrise the model. Costs will include costs of tests and costs after followup, which will include adverse effects of the tests and costs of treatment and management of prostate cancer. These data will come from the trial and from existing sources e.g. NHS reference costs. Data will also include specificity and sensitivity of the tests (from the trial), incidence and risk of progression of the disease (assembled from the literature). The clinical and epidemiological data will be used to calculate path probabilities, combined with EQ-5D utility scores assembled from the literature to allow the estimation of QALYs.

Both probabilistic and deterministic sensitivity (to explore other forms of uncertainty e.g.to explore variations in management, in costs or utility values) analysis will be conducted with the results presented as cost/QALY plots and cost-effectiveness acceptability curves.

Resource impact assessment

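### The economic model takes absolute MRI sensitivity and specificity from the trial, but biopsy depends on the MRI result, so the trial does not identify them without untestable assumptions

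*Protocol*

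**What the plan says.** In section 8.3, Model based analysis, the inputs of the lifetime model are given sources: "Data will also include specificity and sensitivity of the tests (from the trial". Progression and utilities are to come from the literature. The same part says that trial and secondary data will be combined: "Data from the trial and secondary sources such as existing systematic reviews, primary evidence and other".

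The within-trial analysis states: "A within trial cost-effectiveness analyses will estimate the incremental cost per true positive detected and incremental cost per correct diagnosis". Of its accuracy inputs it says: "Estimates of diagnostic performance will be based on the trial analysis". Sections 2.2 and 2.4 list incremental cost per correct diagnosis as an objective and an endpoint.

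Section 5 sets who has a disease status. Scores 4 and 5 are advised a biopsy. For the others, "Patients with a non-suspicious (score 1, 2) or equivocal MRI (score 3" begins a rule under which men with at least one risk factor may be offered one. For men not biopsied, "Patients will be discharged back to the GP by their clinical team after their MRI". Section 5.2 caps follow-up at 12 weeks from enrolment, and section 5 makes long-term linkage conditional on further funding. The protocol gives no share of MRI-negative men expected to be biopsied.

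**The concern.** Sensitivity needs the cancers among MRI-negative men (false negatives), and specificity needs the cancer-free men among them (true negatives). Here verification depends on the test result and on risk factors that themselves predict cancer, which is partial verification. Trial data alone cannot separate a test that misses few cancers from one that misses more among men who are never biopsied.

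The stake is the economic conclusion. Section 8.3 offers the cost-utility analysis as the safeguard if the trial does not rule out important differences, and says that the model will carry the consequences of wrong decisions. Both depend on false negatives. If these are understated, the harm of a less sensitive scan is understated too.

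**Working it through.** **Plan's own figure.** The protocol states no trial-based sensitivity or specificity to reproduce. Its sample size does reproduce: 2 × 0.38 × 0.62 × (1.645 + 1.282)² / 0.05² gives 1,615 per arm after rounding up, 3,230 in all. The point does not touch it.

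**Inputs.** Sensitivity 95% and specificity 38% for mpMRI are from section 1 (paired cohort with template mapping biopsies). Assumed: prevalence 40%; a less sensitive test at 85% with the same specificity; a share v of MRI-negative men biopsied; all MRI-positive men biopsied. With 95% and 38%, these imply 0.40 × 0.95 = 38.0% detection through MRI-positive men and 75.2% MRI-positive. Section 8.1 has 38% detection and 70–75% recommended for biopsy.

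**Cells, as a share of the arm.**

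| Sensitivity | TP | FN | FP | TN |
|---|---|---|---|---|
| 95% | 0.380 | 0.020 | 0.372 | 0.228 |
| 85% | 0.340 | 0.060 | 0.372 | 0.228 |

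**Step 1: non-identification.** Hold 75.2% MRI-positive and 38% detected fixed, with no MRI-negative man biopsied. Let r be the cancer risk in the 24.8% who are MRI-negative. Sensitivity = 0.38 / (0.38 + 0.248r) and specificity = 0.248(1 − r) / [0.248(1 − r) + 0.372]. As r goes from 0 to 30%, sensitivity runs from 100% to 84% and specificity from 40% to 32%. The observed data are the same throughout.

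**Step 2: apparent sensitivity.** Only a share v of false negatives is seen, so apparent sensitivity = TP / (TP + v·FN). This holds whether unbiopsied men are left out or counted as cancer-free.

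| v | True 95% reads | True 85% reads |
|---|---|---|
| 0 | 100% | 100% |
| 10% | 0.380/0.382 = 99.5% | 0.340/0.346 = 98.3% |
| 30% | 98.4% | 95.0% |
| 50% | 97.4% | 91.9% |

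At v = 10%, a 10-point fall shows as 1.2 points.

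**Step 3: correct diagnoses if unbiopsied men count as cancer-free.** The true share is 1 − FP − FN: 60.8% against 56.8%, a loss of 4.0 points. The apparent share is 1 − FP − v·FN: at v = 10%, 62.6% against 62.2%, a loss of 0.4. With equal FP the apparent loss is v times the true one, so 1.2 points at v = 30% and 2.0 at v = 50%.

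**Step 4: what randomisation recovers.** Correct = TP + TN = TP + (1 − prevalence) − FP. Prevalence is equal between arms in expectation, so the increment is ΔTP − ΔFP. Here that is (0.340 − 0.380) − 0 = −4.0 points, the true value, with no MRI-negative man verified. The ratio of sensitivities is also recovered: 0.340/0.380 = 0.895 = 0.85/0.95.

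**Step 5: can the trial correct itself?** At v = 10%, about 1,615 × 0.248 × 0.10 = 40 MRI-negative men per arm are biopsied, with about 3 cancers. The 95% interval for 3/40 is 1.6% to 20.4%, which puts corrected sensitivity between 99% and 88%, even if those biopsied are representative. If they carry twice the risk of those not biopsied, a correction that ignores risk factors centres on 91% instead of 95%.

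**The case against.** The strongest reply is that the listed economic endpoint is incremental. By Step 4, incremental correct diagnoses need only true and false positives, both seen in biopsied MRI-positive men, so there is no reason to drop it. That stands. So does the reply that any excess of cancers missed by bpMRI lowers detection in its arm, which is the primary endpoint.

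Some stronger readings are tempting but not supported:

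- **That accuracy cannot be estimated at all.** Some MRI-negative men are biopsied on recorded risk factors, so an adjusted correction is possible, though imprecise and dependent on assumptions.
- **That having one MRI type per man is the cause.** Parallel arms with full verification would give both accuracies. Only the paired comparison is lost.
- **That specificity would collapse.** Among biopsied men only, it would read 0.0228/0.3948 = 5.8% at v = 10%, but the protocol nowhere states that estimator. The one rule it gives, for missing outcomes in the primary analysis, counts them as no significant cancer. Applied here, it leaves specificity nearly right (39.8% against 38%) but not sensitivity.
- **That the primary objective is untestable because it asks whether bpMRI "is able to accurately rule-out and detect clinically significant prostate cancer".** The objective is comparative and is carried by detection and biopsy rates in each arm.

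It can also be said that correction methods belong in an analysis plan and that the model already draws on secondary sources. A correction method could indeed wait. But the protocol does more than stay silent: it names the trial as the source of absolute accuracy, and that statement needs changing.

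**Conclusion.** The point holds for absolute sensitivity, absolute specificity and the count of missed cancers. As written, the stated source would give the lifetime model sensitivity that is too high and a muted contrast between tests: 1.2 points in place of 10, and 0.4 in place of 4.0 for correct diagnoses if unbiopsied men are counted as cancer-free. These sizes rest on the assumed 40% prevalence, 38% specificity and 10% of MRI-negative men biopsied. They shrink as that share rises, but at 50% half of the loss in correct diagnoses is still hidden. That most MRI-negative men go unbiopsied is an inference from the biopsy rule and the 70–75% recommended for biopsy, not a stated figure.

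Detection rates, relative detection between arms, cost per significant cancer detected, the primary endpoint and the sample size are unaffected. This is a correction to the economic plan that should be made, not a flaw in the trial's main comparison.

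**What to change.** 1. In section 8.3, Model based analysis, replace the statement that sensitivity and specificity come from the trial. Take absolute mpMRI accuracy from fully verified external evidence, with its uncertainty. Take the bpMRI-versus-mpMRI difference from the trial's randomised MRI-positivity, biopsy and detection rates by arm. Do not import the difference from the paired cohorts: sections 1 and 3 justify the trial by the reporter and incorporation bias in such comparisons.
2. Add a sensitivity range for missed cancer in unbiopsied men.
3. Keep incremental cost per correct diagnosis, but define its denominator as the between-arm difference in true positives minus the difference in false positives. This is valid when MRI-positive men are biopsied, so handle declined biopsies in sensitivity analysis. Never count unbiopsied men as correct diagnoses.
4. Fix the score that counts as test-positive. Section 4.1 groups score 3 with suspicious findings for randomisation 2, while section 5 calls it equivocal with conditional biopsy. These passages must be reconciled.

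The cost is wording in the protocol and the health-economics plan, with no new data collection, since the model already combines secondary sources. The downside is that absolute accuracy then rests partly on external data and carries wider uncertainty. The external reference test (template mapping) is not the trial's biopsy, and section 1 does not give the significance threshold behind the 95% and 38%, so that match must be checked.

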9. REGULATORY, ETHICAL AND LEGAL ISSUES

9.1 Declaration of Helsinki

The investigator will ensure that this study is conducted in full conformity with *[* the seventh revision of the 1964 Declaration of Helsinki.

9.2 Good Clinical Practice

The study will be conducted in accordance with the guidelines laid down by the International Conference on Harmonisation for Good Clinical Practice (ICH GCP E6 guidelines).

9.3 Research Ethics Committee (REC) Approval

(i) Initial Approval

Prior to the enrolment of subjects, the REC must provide written approval of the conduct of the study at named sites, the protocol and any amendments, the Subject Information Sheet and Consent Form, any other written information that will be provided to the subjects, any advertisements that will be used and details of any subject compensation.

(ii) Approval of Amendments

Proposed amendments to the protocol and aforementioned documents must be submitted to the REC for approval as instructed by the Sponsor. Amendments requiring REC approval may be implemented only after a copy of the REC's approval letter has been obtained. Amendments that are intended to eliminate an apparent immediate hazard to subjects may be implemented prior to receiving Sponsor or REC approval. However, in this case, approval must be obtained as soon as possible after implementation.

(iii) Annual Progress Reports

Annual Progress Reports will be submitted to the Research Ethics Committee (REC) and the Sponsor in accordance with local / national requirements. The Annual Progress Report will also detail all SAEs recorded.

(iv) End of Trial Notification

The REC will be informed about the end of the trial, within the required timelines.

9.4 HRA approval

Health Research Authority (HRA) approval will be obtained prior to starting the study. Each participating site will confirm capacity and capability prior to commencing. The HRA and all participating sites also need to be notified of all protocol amendments to assess whether the amendment affects the institutional approval for each site.

9.5 Non-Compliance and Serious Breaches

All protocol deviations and protocol violations will be reported via the eCRF and reviewed by the Chief Investigator and reported to the ICTU QA manager on a monthly basis. Protocol violations will be reported to the Sponsor.

An assessment of whether the protocol deviation/violation constitutes a serious breach will be made.

A serious breach is defined as:

A breach of the conditions and principles of GCP in connection with a trial or the trial protocol, which is likely to affect to a significant degree:

- The safety or physical or mental integrity of the UK trial subjects; or
- The overall scientific value of the trial

The Sponsor will be notified within 24 hours of identifying a likely Serious Breach. If a decision is made that the incident constitutes a Serious Breach, this will be reported to the REC within 7 days of becoming aware of the serious breach.

